8.16.4. Observation and Recording of SAEs

All SAEs must be reported to Novella within 24 hours of first awareness of the event.

Additional follow-up information, if required, or available, should be recorded on a follow-up SAE Report Form and faxed to Novella Drug Safety within one business day of discovery by site.

All SAEs, whether related or unrelated to study drug, will be recorded from the time of signed informed consent until resolution or new therapy initiated or for 28 days post final dose if no new therapy is initiated. Any SAEs considered to have at least a possible relationship to the study drug and discovered by the Investigator at any time period after the subject's study treatment has ended should be reported according to the timeframe described above.

Study drug-related SAEs will be followed until resolution, stabilization or subject receives new therapy.

At a minimum, the site number, Investigator's name, subject number, event name, the date of onset, a short description of the event and the Investigator's preliminary assessment of causality must be provided at the time of the initial SAE report.

The onset date of the SAE is defined as the onset date of signs and symptoms or a change in baseline when the SAE met seriousness criteria.

The resolution date of the SAE is defined as the date in which the criteria of seriousness is no longer applicable (e.g., discharge from hospitalization).

All SAEs that are ongoing events at the time of death should be considered not resolved at time of death.

The Investigator is encouraged to discuss with the Medical Monitor any SAEs for which the issue of reportability is unclear or in question.

The Investigator must review, sign, and date the SAE Report Form to confirm the accuracy of the information recorded on the SAE Report Form along with the corresponding source documentation.

8.17. Regulatory Authorities and IRBs

Jounce or its designee is responsible for notifying the investigational sites and all health authorities (e.g. FDA) of all expedited SAEs.

The Investigator will notify his or her IRB of serious, related and unexpected AE(s) or significant risks to subjects. The Investigator must keep copies of all AE information, including correspondence with Jounce or Local Ethics Committees on file.

It is the responsibility of the Principal Investigator (PI) to notify the IRB of all SAEs that occur at his or her site as per site guidelines. Investigators will be notified of all suspected, unexpected SAEs (7/15 Day Safety Reports) that occur during any clinical studies that are using the investigative compound. Each site is responsible for notifying its IRB/EC of these additional SAEs.

9. STATISTICAL ANALYSES

9.1. Endpoints

The following endpoints will be used to measure the efficacy, safety, and exploratory objectives of the study.

9.1.1. Safety Endpoints

The following safety endpoints will be assessed:

- Incidence and severity of treatment-emergent adverse events;
- Incidence and severity of treatment-emergent changes in clinical laboratory values;
- Incidence of dose limiting toxicities;
- Incidence of anti-drug antibodies to JTX-2011 and/or nivolumab, ipilimumab, or pembrolizumab;
- Incidence of neutralizing antibodies to JTX-2011 and/or nivolumab, ipilimumab, or pembrolizumab;
- Incidence of decreases in ECOG performance status;
- Incidence of clinically significant changes in ECG measurements.

9.1.2. Efficacy Endpoints

Efficacy will be evaluated using RECIST v1.1 (Section 12.4) and immune-related Response Criteria (irRC) (Section 12.7), or for modified RECIST only for subjects with mesothelioma (Section 8.7) with the following endpoints:

- Overall Response Rate: % of subjects with Complete Response (CR) plus Partial Response (PR);
- Duration of Response in months;
- Disease Control Rate: % of subjects with Complete Response + Partial Response + Stable Disease;
- Landmark Progression Free Survival Rate at 6 months and 12 months;
- Progression Free Survival.
- Landmark Overall Survival at 6 months and 12 months;
- Overall Survival.

9.1.3. Pharmacokinetic Endpoints

PK endpoints are for JTX-2011 unless otherwise specified. The following PK endpoints will be determined (if feasible):

- Maximum observed concentration (C_{max}) of JTX-2011, nivolumab, ipilimumab and/or pembrolizumab in serum for all treatment cycles;
- Minimum measured concentration (C_{min}) of JTX-2011, nivolumab and/or pembrolizumab in serum for treatment cycles >1);
- Time from dosing to maximum measured concentration (t_{max});
- Area under the serum concentration-time curve over the dosing interval ($AUC_{0-\tau}$)

- Area under the serum concentration-time curve over the time interval from 0 to 336 hours after dosing (AUC_{0-336}) for nivolumab, in order to compare nivolumab PK to PK in literature in which nivolumab is dosed q2w);
- Area under the concentration-time curve of from time 0 extrapolated to infinity ($AUC_{0-\infty}$) JTX-2011, nivolumab, ipilimumab and/or pembrolizumab in serum over the time interval from 0 extrapolated to infinity);
- Percentage of $AUC_{0-\infty}$ obtained by extrapolation from the last evaluable time point ($\%AUC_{12-\infty}$);
- Terminal rate constant in serum (λ_z);
- Terminal half-life of JTX-2011 or nivolumab in serum ($t_{1/2}$);
- Mean residence time (MRT_{iv}) of JTX-2011, nivolumab, ipilimumab and/or pembrolizumab in the body after intravenous infusion);
- Total clearance (CL) of the analyte in serum after intravenous infusion;
- Apparent volume of distribution (V_z) during the terminal phase λ following intravenous infusion;
- Apparent volume of distribution at steady state following intravenous infusion (V_{ss}).
- Assess impact of ADA on PK

9.1.4. Pharmacodynamics Endpoints

The following pharmacodynamics endpoints will be determined (if feasible):

- Percent target engagement at each time point of pharmacodynamics marker measurement;
- Maximum % target engagement in serum (E_{max}) and minimum % target engagement in serum (E_{min});
- Area under the effect-time curve of the pharmacodynamics marker in serum over the time interval from t_1 to t_2 ($AUEC_{t_1-t_2}$), where t_2 is 8 days, 15 days, and 21 days after the first dose of JTX-2011).

9.2. Exploratory Endpoints

9.2.1. Safety

The following safety exploratory endpoints will be assessed (if feasible):

- Incidence and severity of increase in inflammatory cytokines;
- Change in peripheral blood lymphocyte subsets.

9.2.2. Predictive

Efficacy endpoints will be assessed for correlation with the following exploratory predictive biomarkers, if samples are available:

- ICOS IHC score;
- Predefined ICOS RNA signature;
- Exploratory RNA signature;
- DNA mutational load;
- Neoantigen expression;

- PD-L1 IHC score.

9.2.3. Mechanistic

The following mechanistic exploratory endpoints will be assessed (if feasible):

- Change in peripheral blood immune cell gene signatures;
- Change in intratumoral immune cell gene signatures;
- Change in intratumoral immune cell subsets.

9.3. Statistical Basis for Sample Size

[figure not shown]
Approximately 380 evaluable subjects will be enrolled in 4 parts of the study.

For **Part A**, **Part B**, **Part E**, and **Part G**, the choice of the number of subjects was based on the classical 3 + 3 design. The approximate sample size in the dose escalation cohorts in Part A will be 36 evaluable subjects assuming that 6 subjects are assigned at each of 6 planned dose levels. The approximate sample size of the dose escalation cohorts in Part B will be 24 evaluable subjects assuming that 6 subjects are assigned at each of 4 planned dose levels. The approximate sample size of the dose escalation cohorts in Part E will be 18 evaluable subjects assuming that 6 subjects are assigned at each of 3 planned escalation dose levels. The approximate sample size of the dose escalation cohorts in Part G will be 12 evaluable subjects assuming that 6 subjects are assigned at each of 2 planned dose levels. The dose escalation will stop at the dose level at which 2 subjects experience any of the defined DLTs, which would avoid selecting a dose level with > 33% chance of observing a DLT into further development.

Approximately 8 subjects are planned to be added to each of 2 (or more) dose levels in Parts A (AP1, AP2) and B (BP1, BP2) where 70% target engagement is observed in 2/3 subjects at either Day 8 or Day 21 (see Section 6.4), to obtain additional safety and PK/PD data. This addition will yield a total of 11 (or 14) subjects on the same dose level, providing at least 70% chance to observe 4 or more targeted toxicities if the true toxicity rate is 0.3 or more for the dose.

Subjects may also be added if the exploration of intermediate dose level(s) of JTX-2011 is warranted or if the SMC recommends adding additional subjects at a given dose level to further understand and clarify safety issues.

In **Part C**, **Part D**, **Part F** and **Part H** the preliminary efficacy signal, measured by the overall response rate (ORR), will be evaluated using a group sequential design with 1 interim look for futility. The following hypotheses $H_0: ORR \leq 0.08$ versus $H_1: ORR \geq 0.20$ will be tested with a 90% power at a 2-sided $\alpha=5\%$. As the first step, 15 (Part C) or 15 (Part D) or 15 (Part F) or 15 (Part H) subjects will be enrolled for each cohort in the current protocol. The anticipated total sample size for each cohort could be as large as 76 if warranted by the result obtained from the first 20 or 15 subjects. The following table lays out different scenarios based on the observed ORR from the first 20 or 15 subjects within each cohort:

Table 10: Operating Features of A Group Sequential Design with 1 Futility Interim Look at 20 or 15 Subjects with 90% Power and 2-sided $\alpha=5\%$.

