Of note, Parts A and B both have pharmacokinetic/pharmacodynamic (PK/PD) expansion cohorts which don't follow the naming conventions described above, instead they are labeled as API, BPI, etc.

PROTOCOL SYNOPSIS

Study Title:	Phase 1/2 Multicenter Trial of ICOS Agonist Monoclonal Antibody (mAb) JTX-2011 Alone and in Combination with Nivolumab, Ipilimumab, or Pembrolizumab in Adult Subjects with Advanced and/or Refractory Solid Tumor Malignancies
Protocol Number:	JTX-2011-101
Sponsor:	Jounce Therapeutics, Inc.
Phase of Development:	Phase 1/2; First-in-human
Objectives for Phase 1: Parts A, B, E, and G	Primary Objectives 
 Assess the safety and tolerability of JTX-2011 monotherapy (Part A), JTX-2011 in combination with nivolumab (Part B), JTX-2011 in combination with ipilimumab (Part E), and JTX-2011 in combination with pembrolizumab (Part G) in subjects with advanced and/or refractory solid tumor malignancies after single and multiple ascending doses; Determine the maximum tolerated dose (MTD) and the recommended Phase 2 dose (RP2D) of JTX-2011 (Part A), JTX-2011 in combination with nivolumab (Part B), JTX-2011 in combination with ipilimumab (Part E), and JTX-2011 in combination with pembrolizumab (Part G) in subjects with advanced and/or refractory solid tumor malignancies.
	Secondary Objectives 
 Assess the pharmacokinetics (PK) and pharmacodynamics (PD) of single and multiple ascending doses of JTX-2011 when administered as monotherapy (Part A), JTX-2011 in combination with nivolumab (Part B), JTX-2011 in combination with ipilimumab (Part E), and JTX-2011 in combination with pembrolizumab (Part G); Assess the PK of nivolumab when administered in combination with JTX-2011 (Part B); Assess the PK of ipilimumab when administered in combination with JTX-2011 (Part E); Assess the PK of pembrolizumab when administered in combination with JTX-2011 (Part G).
	Exploratory Objectives 
 Evaluate the effect of JTX-2011 monotherapy (Part A), JTX-2011 in combination with nivolumab (Part B), JTX-2011 in combination with

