6.2. Dose Escalation Scheme

In Part A, six (6) dose escalation cohorts were explored, 0.003 mg/kg, 0.01 mg/kg, 0.03 mg/kg, 0.1 mg/kg, 0.3 mg/kg, and 1 mg/kg. In Part B, four (4) dose escalation cohorts were explored, 0.01 mg/kg, 0.03 mg/kg, 0.1 mg/kg, 0.3 mg/kg.

In Parts E and G, each dose escalation cohort will consist of a minimum of 3 subjects. The first subject in each dose cohort will receive JTX-2011 + ipilimumab or + pembrolizumab, respectively, on CID1 (sentinel subject) and be monitored for at least 72 hours as an outpatient until acute and subacute safety is confirmed. If, after 72 hours, there are no safety concerns, the

next two subjects in the dose cohort will be allowed to enroll in parallel (if the Investigator and Sponsor agree, then no SMC review will be required). Note: hospitalization is not required).

If, after 72 hours, there are no safety concerns, the next two subjects in the dose cohort will be allowed to enroll in parallel (if the Investigator and Sponsor agree, then no SMC review will be required).

The first 3 or 6 subjects at each dose-level will be assigned according to the classical 3 + 3 design, as follows. If:

- 0 of 3 subjects in a cohort experiences a DLT, then the next higher dose-level cohort may be enrolled.
- 1 of 3 subjects in a cohort experiences a DLT, then enrollment into that cohort will be expanded to a total of 6 subjects.
- 1 of 6 subjects in an expanded cohort experiences a DLT, then the next higher dose-level cohort may be enrolled.
- >1 of 3-6 subjects in a cohort experience a DLT, then the MTD has been exceeded and further enrollment into that cohort will cease. Using the same criteria, additional cohorts may then be explored until the MTD has been determined, including intermediate doses.

Subjects in each cohort must complete the first cycle of each cohort through C2D1 assessments or have experienced a DLT to be considered evaluable; non-evaluable subjects will be replaced.

Once a RP2D is determined for a particular part of the trial, subjects at lower doses in that part who remain on study treatment and are tolerating it well may increase their dose to the RP2D. In addition, the SMC will be convened approximately every 3 months to review accumulating safety data and patient disposition by cohort through the duration of the study.

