6.2.2. Criteria for Proceeding to the Next Dose Level

Depending upon the dosing schedule being tested in dose escalation, the Safety Monitoring Committee (SMC) will review all safety data available through at least 2 weeks (in q3w dosing) or 5 weeks (q6w dosing) and make an initial dose escalation recommendation. Enrollment in the next dose escalation cohort may occur after:

- SMC determines that there are no safety concerns with review of ≥ 14 days data for all evaluable subjects within a cohort;
- All subjects within a dose cohort complete ≥ 1 cycle;
- DLT observed in < 1 out of 3 evaluable subjects (or < 2 out of 6 evaluable subjects) during Cycle 1;
- SMC agrees that no additional subjects are required in the current cohort to further define safety.

Following the review of safety data obtained at a given dose level, the SMC will convene via telephone conferences and decide the dose level for the next cohort. If potential safety signals are identified, the administration of interim dose levels (e.g., increment of $< 25\%$ of current dose level instead of 25-50%) may be recommended. In addition, to enable accurate and appropriate clinical and scientific interpretation of the data, a dose level may be repeated as requested by the SMC. Dose escalation will be recommended only if a consensus to escalate is reached by the SMC after review and discussion of the current dose level's safety data.

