6.5. Safety/PK/PD Expansion Cohorts (AP1, AP2, BP1, BP2)

At each of two or more dose levels, approximately eight additional subjects will be enrolled for additional safety and PK/PD data. These subjects will be required to have biopsies of their tumors at baseline and after completion of 2 cycles of JTX-2011 for pharmacodynamics assessments. These subjects may be enrolled before, during, and after enrollment has commenced in Part C or D.

First Safety/PK/PD Expansion Cohort: If safety data are acceptable, Part A Safety/PK/PD Expansion Cohort 1 (AP1) and Part B Safety/PK/PD Expansion Cohort 1 (BP1) will be initiated at the first dose level of that Part at which there is approximately 70% Target Engagement (TE) in 2/3 subjects on Day 8.

Second Safety/PK/PD Expansion Cohort: If safety data are acceptable, Part A Safety/PK/PD Expansion Cohort 2 (AP2) and Part B Safety/PK/PD Expansion Cohort 2 (BP2) will be initiated at the lowest dose level at which there is approximately 70% TE in 2/3 subjects on Day 21, the MTD, or the highest dose studied.

The SMC will review safety data as outlined in the dose escalation phase for aggregate AEs for 9 weeks (e.g. through Cycle 3). Once a RP2D is determined, subjects at lower doses who remain on study treatment and are tolerating it well may increase their dose to the RP2D. In addition, the SMC will be convened approximately every 3 months to review accumulating safety data and patient disposition by cohort through the duration of the study.

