6.6. Definition of Maximum Tolerated Dose and Recommended Phase 2 Dose

The MTD is defined as the JTX-2011 dose level that yields the largest estimated toxicity rate below 33%.

The RP2D, as well as administration time (currently a one-hour IV infusion each for JTX-2011 and nivolumab, 1.5-hour infusion for ipilimumab, and 30-minute infusion for pembrolizumab) and schedule will be determined in discussion among the Sponsor and Investigators. Observations related to safety, PK, pharmacodynamics, and IV infusion tolerability will be included in the rationale supporting the RP2D and schedule.

Observations related to safety, PK, pharmacodynamics, and IV infusion tolerability will be included in the rationale supporting the RP2D and schedule.

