#### 6.1.1 SUBSETS OF THE SAF

- Response Evaluable Set: subjects in SAF who have a baseline tumor assessment, and either has at least one post-baseline tumor assessment scan and/or discontinued treatment due to death or disease progression.
- The DLT Evaluable Set: SAF subjects in Phase 1 parts (A, B, E, G) who receive at least one dose of JTX-2011 during the DLT-evaluation period (1st cycle) and complete the DLT-evaluation period (1st cycle) or experience any DLTs.
- Biomarker Analysis Set: SAF who have a baseline sample and at least one post treatment biomarker sample.
- ADA Analysis Set: SAF who have a baseline sample and at least one post treatment ADA sample.

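### Section 9.3 says the two-DLT stop avoids doses with more than a 33% DLT chance, but the 3+3 rule clears a tested dose with a true 40% DLT rate 31% of the time

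*Protocol*

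**What the plan says.** Protocol Section 9.3 bases the Phase 1 sample sizes on the classical 3+3 design. It adds that escalation stops at the level where 2 subjects have DLTs, "which would avoid selecting a dose level with > 33% chance of observing a DLT into further development". No error probability is attached to that statement.

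The clearance rule is in Section 6.2. A level clears on 0 DLTs in 3 subjects. One in 3 leads to expansion to 6, and then "1 of 6 subjects in an expanded cohort experiences a DLT, then the next higher dose-level cohort may be enrolled". Section 6.2.2 gives the same limits: "DLT observed in < 1 out of 3 evaluable subjects (or < 2 out of 6 evaluable subjects) during Cycle 1".

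Section 9.3 also plans about 8 further subjects at chosen levels in Parts A and B: "This addition will yield a total of 11 (or 14) subjects on the same dose level". The naming conventions place these cohorts in the same two parts ("Parts A and B both have pharmacokinetic/pharmacodynamic (PK/PD) expansion cohorts"). None are planned in Parts E and G.

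Section 6.6 and the synopsis state: "The MTD is defined as the JTX-2011 dose level that yields the largest estimated toxicity rate below 33" percent. They give no estimator and no outcome for an MTD that is not reached. SAP Section 9.9.1 tabulates DLTs and adds no MTD rule.

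**The concern.** Section 9.3 attributes a safety property to the stopping rule: a dose whose DLT probability exceeds 33% will not go forward. Investigators and IRBs may rely on that sentence. With 3 to 6 subjects per level, a rule that passes 0/3 or 1/6 cannot separate a 25% rate from a 40% rate with much certainty, so a good share of overly toxic levels would be expected to pass.

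Determining the MTD is a primary Phase 1 objective. A definition that ranks levels by estimated toxicity rather than by dose may not agree with the escalation rule that produced the data.

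**Working it through.** The plan gives no figure for the 33% statement, so there is none to reproduce. The one toxicity probability in Section 9.3 concerns the expansion cohorts, not this rule.

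**Clearance of a tested level.** Inputs: clear on 0/3, or on 1/3 followed by 0/3 (Sections 6.2 and 6.2.2). For a true DLT rate p,

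P(clear) = (1−p)³ + 3p(1−p)² × (1−p)³ = (1−p)³ + 3p(1−p)⁵.

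As a sensitivity check, suppose six subjects with at most 1 DLT were always required, since Section 9.3 counts 6 per level: (1−p)⁶ + 6p(1−p)⁵.

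| True rate p | (1−p)³ | 3p(1−p)⁵ | Cleared, 3+3 | At most 1 of 6 |
|---|---|---|---|---|
| 33% | 0.301 | 0.134 | 0.434 | 0.358 |
| 40% | 0.216 | 0.093 | 0.309 | 0.233 |
| 50% | 0.125 | 0.047 | 0.172 | 0.109 |

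(Components are rounded separately.)

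**Illustration with expansion, Parts A and B only.** Assume that after 8 added subjects the pooled observed rate must stay below 33%. The protocol does not state this rule. From 0/3 the limit is 3/11 (27%; 4/11 is 36%). From 1/6 it is 4/14 (29%; 5/14 is 36%). Either way, at most 3 of the 8 may have a DLT, so the probability is P(clear) × P(Bin(8,p) ≤ 3):

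- p = 33%: 0.434 × 0.748 = 0.325
- p = 40%: 0.309 × 0.594 = 0.184
- p = 50%: 0.172 × 0.363 = 0.062

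**Reaching the level first.** P(clear) is 0.906 at p = 10% and 0.709 at p = 20%. With assumed true rates of 10/20/40%, reaching and clearing the 40% level has probability 0.906 × 0.709 × 0.309 = 0.199. With 20/40% it is 0.709 × 0.309 = 0.219. Other assumed lower-dose rates gave 12% to 28%.

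**Section 6.6 read literally.** Take the estimated rate as the raw rate in the 3 or 6 escalation subjects, and consider three levels with the third exceeded. If level 1 cleared at 1/6 and level 2 at 0/3, the largest rate below 33% belongs to level 1, although level 2 was cleared. The probability, as a share of all trials, is 3p₁(1−p₁)⁵ × (1−p₂)³ × [1 − P(clear at p₃)]:

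- rates 5/10/15%: 0.116 × 0.729 × 0.186 = 0.016
- rates 10/20/30%: 0.177 × 0.512 × 0.506 = 0.046

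With two levels, as planned in Part G, this cannot happen.

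**The case against.** The strongest defence is that the sentence describes the observed rate. A cleared level shows 0/3 or 1/6, and 2/6 is already 33%, which fits the 33% limit in Section 6.6. However, Section 9.3 refers to the chance of observing a DLT, which is the true probability, and to what goes into further development. It is fair that no document states a guarantee, and that this is a familiar property of 3+3 designs.

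The second defence is that clearance is not selection. This stands. The SMC escalates only by consensus and may add subjects (Section 6.2.2), may declare further DLTs (Section 6.3) and reviews 9-week aggregate AEs (Section 6.1.1). The RP2D rests on safety, PK, pharmacodynamics and tolerability (Section 6.6). Confirming safety, MTD and RP2D is a primary objective of Parts C and D (Section 2.2.1). The documents do not say how far these steps lower the figures, and Section 9.3 credits the two-DLT stop, not these steps.

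Third, practical reach is limited. SAP Section 4 says that all Phase 1 parts are completed and that Parts F and H never opened. The lack of expansion cohorts in Parts E and G therefore had no Phase 2 consequence in this trial.

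On the MTD, Section 6.2 implies dose order, and Section 6.5 already allows for "the MTD, or the highest dose studied". A reader might infer that ties make the definition unworkable. Under the assumed curves, ties arise in 12.0% and 20.6% of trials, but 11.6 and 18.9 of those points are 0/3 against 0/3, which dose order settles.

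**Conclusion.** The Section 9.3 sentence is wrong as written. The 3+3 rule clears a tested level with probability 43%, 31% or 17% at true DLT rates of 33%, 40% or 50%. Requiring six subjects lowers these to 36%, 23% and 11%, which still does not amount to avoidance. The figures assume only independent DLTs at a common rate and that the level is tested.

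A reader might infer that the trial had a 31% chance of taking a 40% dose forward, or that 18% is the design's property in Parts A and B. Neither follows. The 31% precedes every later safeguard and is conditional on testing the level; the 18% depends on a pooled rule that the protocol does not contain. Recorded expansion enrolment was also 12 subjects over AP1 and AP2 and 15 over BP1 and BP2 (Sections 5.1 and 5.2), not exactly 8 per level. Nor do the documents suggest a mis-selected RP2D: Part A explored 1 mg/kg and the RP2D was 0.3 mg/kg.

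The MTD definition is a minor point. A lower dose is named in 1.6% to 4.6% of trials, under assumed curves and a raw-rate estimator. The effect of both points is on the stated safety property and the reported MTD.

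**What to change.** In Section 9.3, replace 'would avoid selecting' with 'limits the chance of selecting', and add: 'The 3+3 rule clears a tested level with probability 43%, 31% or 17% at true DLT rates of 33%, 40% or 50%, before SMC review, added or expansion subjects and the RP2D decision.' If the 18% at a 40% true rate is quoted, label it as an illustration for Parts A and B under an assumed pooled rule of below 33%.

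In Section 6.6 and the synopsis, define the MTD as the highest dose level cleared under Section 6.2 at which the observed DLT rate among all DLT-evaluable subjects at that level is below 33%, provided a higher level was exceeded. Count a level as exceeded if it fails Section 6.2 or if its pooled observed DLT rate is 33% or more. Report 'MTD not reached', with the highest dose studied, only if no level is exceeded in either sense. If a level is exceeded and none qualifies, say that no studied dose met the definition.

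The pooled limb is needed. A top level cleared at 1/6 that then has 4 DLTs in 8 expansion subjects ends at 5/14 (36%). Under Section 6.2 alone it would be reported as MTD not reached.

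Repeat the rule in SAP Section 9.9.1, using the DLT Evaluable Set of SAP Section 6.1.1 ("SAF subjects in Phase 1 parts (A, B, E, G) who receive at least one dose of JTX-2011 during the DLT-evaluation period"), which is not limited to escalation cohorts.

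The cost is wording in three places in the protocol and one SAP rule. The stated safety property becomes less favourable. No patients are added and no past dosing decision changes.

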## 5. SAMPLE SIZE CONSIDERATIONS

For Part A, Part B, Part E, and Part G, the choice of the number of subjects is based on the classical 3 + 3 design. The approximate sample size in the dose escalation cohorts in Part A will be 36 evaluable subjects assuming that 6 subjects are assigned at each of 6 planned dose levels. The approximate sample size of the dose escalation cohorts in Part B will be 24 evaluable subjects assuming that 6 subjects are assigned at each of 4 planned dose levels. The approximate sample size of the dose escalation cohorts in Part E will be 18 evaluable subjects assuming that 6 subjects are assigned at each of 3 planned dose levels. The approximate sample size of the dose escalation cohorts in Part G will be 12 evaluable subjects assuming that 6 subjects are assigned at each of 2 planned dose levels.

Approximately 8 additional subjects will be enrolled in safety/PK/Pharmacodynamics expansion cohorts at each of 2 or more dose levels in Parts A (AP1, AP2) and B (BP1, BP2) to obtain additional safety and PK/Pharmacodynamics data. Subjects may also be added if exploration of intermediate dose level(s) of JTX2011 is warranted or if the SMC recommends adding additional subjects at a given dose level to further understand and clarify safety issues.

Approximately 120 subjects may be enrolled in Part C (approximately 15 in each cohort). Approximately 90 subjects may be enrolled in Part D (approximately 15 subjects per cohort). For Parts C and D, a group sequential design will be used to evaluate the preliminary efficacy of JTX-2011 or JTX-2011 in combination with nivolumab, with an interim look for futility. A 90% power at a 2-sided  $\alpha$  will be achieved for the hypothesis testing by enrolling 15 subjects (no more than 2% of  $\beta$  spent at interim) as the first step, and a potential expansion up to approximately 49 subjects per cohort if the futility boundary is passed based on the result from the first 15 subjects for each cohort. Using the same alpha and a non-binding futility analysis at 40% of evaluable subjects (17) with a Gamma spending function of -3 provides 80% power to rule out 13% in favor of 28%.

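### Protocol 9.3 claims at least a 70% chance of seeing four or more toxicities at a true rate of 0.30; with 11 or 14 subjects the chance is 43% or 64%.

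*Protocol*

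**What the plan says.** Protocol section 9.3 plans about 8 additional subjects at each of two or more dose levels in Parts A and B. On the resulting size it says: "This addition will yield a total of 11 (or 14) subjects on the same dose level". The same sentence then gives the operating characteristic: "providing at least 70% chance to observe 4 or more targeted toxicities if the true toxicity rate is 0.3 or more for the dose".

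The two totals follow from the escalation design. Protocol section 6.2 states that "The first 3 or 6 subjects at each dose-level will be assigned according to the classical 3 + 3 design", and 3 + 8 = 11, 6 + 8 = 14.

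The expansion is described again, without any probability, in Protocol section 6.5 ("At each of two or more dose levels, approximately eight additional subjects will be enrolled for additional safety and PK/PD data"), in Protocol section 9.4.1 and the synopsis, and in SAP section 5 ("Approximately 8 additional subjects will be enrolled in safety/PK/Pharmacodynamics expansion cohorts at each of 2 or more dose levels"). Nothing in either document replaces or corrects the 70%.

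**The concern.** The sentence prints every input needed to check it, and the expected counts already cast doubt on it. At a true rate of 0.30 the expected number of toxicities is 11 × 0.30 = 3.3 or 14 × 0.30 = 4.2. With 11 subjects the threshold of four lies above the mean, so a 70% chance of reaching it is implausible.

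This is the only probability the documents offer for the size of the expansions, and safety is a primary Phase 1 objective. A reader who trusts it expects a 30% toxicity rate to show itself as four or more events at least seven times in ten. If the true chance is much lower, seeing fewer than four events is weaker evidence against a 30% rate than the text implies, so the error runs in the reassuring direction.

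**Working it through.** **Inputs**

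| Input | Value | Source |
|---|---|---|
| Subjects at the dose level, n | 11 or 14 | Protocol 9.3; 3 or 6 from escalation (6.2) plus about 8 |
| Threshold | "4 or more targeted toxicities" | Protocol 9.3 |
| True rate, p | 0.3 or more; lowest case 0.30 | Protocol 9.3 |
| Stated probability | at least 70% | Protocol 9.3 |

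Each subject is treated as having or not having a toxicity, independently, with common rate p. Then

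P(X ≥ 4) = 1 − Σ C(n, k) pᵏ (1 − p)ⁿ⁻ᵏ for k = 0 to 3.

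This increases with p, so a lower bound claimed for all rates of 0.30 and above has to hold at 0.30.

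**Attempt to reproduce the 70% at p = 0.30**

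- n = 11: the terms for 0, 1, 2 and 3 events are 0.0198, 0.0932, 0.1998 and 0.2568, which sum to 0.5696. P(X ≥ 4) = 1 − 0.5696 = **0.4304**.
- n = 14: the terms are 0.0068, 0.0407, 0.1134 and 0.1943, which sum to 0.3552. P(X ≥ 4) = 1 − 0.3552 = **0.6448**.

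The shortfalls are 70 − 43.0 = 27 points and 70 − 64.5 = 5.5 points. The figure is not reproduced at either size.

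**Other methods with the same inputs**

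| Method | n = 11 | n = 14 |
|---|---|---|
| Normal approximation, continuity-corrected | 0.448 | 0.658 |
| Normal approximation, uncorrected | 0.323 | 0.546 |
| Poisson | 0.420 | 0.605 |

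None comes within 2 points of 70%.

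**What would give 70%**

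- Keeping four or more events, the true rate would have to be about 0.398 (n = 11) or 0.319 (n = 14).
- Keeping four or more events at 0.30, the smallest n is 15 (0.7031).
- Changing the threshold to three or more at 0.30 gives 1 − (0.0198 + 0.0932 + 0.1998) ≈ 0.687 for n = 11 and 1 − (0.0068 + 0.0407 + 0.1134) ≈ 0.839 for n = 14.
- Changing the rate to 0.40 with four or more events gives 0.704 (n = 11) and 0.876 (n = 14).

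A threshold of three and a rate of 0.40 are the nearest candidates for the origin of the figure. The documents do not settle which, if either, was meant.

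**Allowing for the escalation result**

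Suppose the toxicities are DLTs and the level was cleared under the 3 + 3 rule. After 0 of 3, four or more of the 8 added subjects must have an event: 0.194. After 1 of 6, three or more of 8 are needed: 0.448. After 0 of 6, which can arise because the safety committee may add three subjects (Protocol 6.1.1), it is again 0.194. Conditioning moves the probability further from 70%.

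**The case against.** The strongest reply is that nothing depends on the sentence. The expansions open on target engagement if safety data are acceptable (Protocol 6.5), the safety committee reviews accumulating data, SAP section 3.3.1 treats safety descriptively, and SAP section 5 does not carry the probability forward. Enrollment in Parts A and B is complete, with 12 subjects in AP1 and AP2 together and 15 in BP1 and BP2 together (Protocol 5.1, 5.2), against roughly 2 × 8 = 16 planned per part. All of this stands, and it limits the point to a minor one. It does not make the sentence true.

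A second reply is that the added number is approximate. One more subject lifts n = 14 to 15 and the probability to 0.703; if three or more was intended, one more lifts n = 11 to 12 and the probability to 0.747. It is fair to say that the only large gap is the 27 points at n = 11 with a threshold of four. But the sentence fixes the totals at 11 and 14, and Part A fell short of the plan. If its 12 subjects were split evenly over two levels, with 6 added to each (an assumption, since the split is not given), the totals would be 9 or 12 and the chance of four or more events 0.27 or 0.51.

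A third reply is that the toxicities being counted are not defined, so the binomial model is itself an assumption. That is correct and is a reason to ask for the definition. The Poisson result shows that dropping the one-outcome-per-subject model does not recover 70%.

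**Conclusion.** The sentence is wrong as written. With the printed inputs, the chance of four or more toxicities at a true rate of 0.30 is 43.0% for 11 subjects and 64.5% for 14, not at least 70%. The claim becomes true only above a rate of about 0.40 (n = 11) or 0.32 (n = 14). Under the most charitable change of threshold, to three or more, it holds for 14 subjects and misses narrowly, by 1.3 points, for 11.

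The result rests on independent subjects with a common toxicity rate and on fixed totals of 11 and 14 before the trial. Severity is minor: the error affects how Phase 1 safety precision is described, not enrollment, any decision rule or any planned analysis.

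**What to change.** Ask the sponsor to confirm the intended threshold and to define the toxicities it counts. Then restate the sentence in Protocol 9.3 or in the sample-size section of the study report.

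- If four or more is intended: *a 43% (n = 11) or 64% (n = 14) chance of observing four or more such toxicities at a true rate of 0.30, as an unconditional pre-trial binomial probability*.
- If three or more was intended: 69% (n = 11) or 84% (n = 14) with the same qualifier, and no claim of at least 70% for 11 subjects.

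The word unconditional is needed because, if the events are DLTs, a dose level that has cleared escalation already has few of them and the remaining probability is lower.

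The cost is one sentence of wording and a less favourable figure. It needs no extra subjects and no change to any rule or analysis.
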